## 8.9. Strengths and limitations of the research methods

The study design is considered to be the main strength of this study. It brings a unique opportunity to compare the outcomes of two cohorts of patients fulfilling the same inclusion criteria. Another strength of the design is data collection in real-world setting without any patient's selection according subgroups characteristics. The main limitation of the research may be a random distribution of patients on warfarin/apixaban treatment.

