Nonetheless NOACs were categorized as a second line treatment due to the restriction of SUKL (local regulatory authority) in Czech Republic and therefore Czech patients are primarily treated with warfarin (including patient post stroke/TIA) and NOACs treatment can be initiated only in case of defined contraindication. Czech Cardiology Society, Society of Ambulatory Specialist together with main Czech Public Insurance House (VZP) defined number of conditions where safe and efficacious anticoagulation therapy by VKA cannot be adequately ensured. Prescription of NOACs as first line therapy is allowed in these defined situations . One of the situations is described as higher sensitivity to warfarin. There are two variants of two genes, CYP2C9 and VKORC1, account for 30-50% of the variability in dosing of warfarin. The prevalence of CYP2C9 (allele \*1, \*2 and \*3) and VKORC1 (-1639 G and A alleles), and their combinations in Czech population was analyzed and about 30% of the Czech healthy subjects have genetically determined higher sensitivity to warfarin. Individuals with higher sensitivity to warfarin are eligible for first line NOACs treatment in secondary prevention of stroke.

Additionally there is no healthcare resource use (hospitalization days, outpatient visits, and clinical events) comparison of apixaban to warfarin available in the Czech Republic. The most intensive resource use is expected in the first 6 months after stroke, especially because of a high risk of the event recurrence. Considering that there are less outpatient visits, less monitoring needed and lower risk of the complications and adverse events expected with apixaban. Real-world data about the impact of different treatment strategies on healthcare resource use and costs are essential arguments for establishing the clinical value of new therapies.

In the light of this situation we have designed this study to compare the healthcare resource use in patients who use warfarin or apixaban in secondary stroke prevention as a first line therapy.

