## 7. RESEARCH QUESTION AND OBJECTIVES

The primary objective of the study is:

- Description of direct costs related to warfarin/apixaban treatment during the first 6 months of the secondary stroke prevention in NVAF patients.

The secondary objectives of this study are:

- Comparison of direct costs related to warfarin/apixaban treatment during the first 6 months of the secondary stroke prevention in NVAF patients;
- Number of hospitalization days in the first 6 months of the treatment;
- Number of ischemic/hemorrhagic strokes in the first 6 months of the treatment;
- Number of ischemic events in the first 6 months of the treatment;
- Number of major/minor hemorrhagic events in the first 6 months of the treatment;
- Mortality rates in both cohorts;
- Number and costs of medical procedures directly related to the treatment in the first 6 months (visits, hospitalizations, labs, diagnostics, etc.);
- Overall safety (adverse events) of the treatment.

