### 8.2.1. Inclusion criteria

The data will be collected for patients who have met all of the following inclusion criteria:

1. Diagnosis of non-valvular atrial fibrillation (NVAF);
2. New initiation of anticoagulation therapy (apixaban or warfarin) due to the ischemic event (stroke/TIA) meaning patients previously not anticoagulated due to diagnosis of NVAF;
3. Indication to anticoagulation therapy as a secondary stroke prevention within 7 to 30 days after the stroke/TIA event;
4. Apixaban arm: genetically determined higher sensitivity to warfarin;
5. Patients whose status allowed oral treatment with apixaban/warfarin;
6. Age  $\geq 18$ ;
7. Access to patient's records of the first 6 months of the warfarin/apixaban treatment.

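### Section 8.9 says both arms meet the same inclusion criteria, although criterion 4 selects only the apixaban arm on warfarin sensitivity; separately, Section 8.7 names paired tests for two cohorts with no pairs defined

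*Combined protocol and SAP*

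**What the plan says.** **On the comparability of the arms.** Section 8.9 presents as a strength that "It brings a unique opportunity to compare the outcomes of two cohorts of patients fulfilling the same inclusion criteria". It adds that real-world data are collected without patient "selection according subgroups characteristics". The one limitation it names is this: "The main limitation of the research may be a random distribution of patients on warfarin/apixaban treatment".

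Section 8.2.1 lists seven inclusion criteria. Six apply to both arms. The fourth reads "Apixaban arm: genetically determined higher sensitivity to warfarin", and the warfarin arm has no corresponding requirement or exclusion. Section 6 gives the background. Under the Czech restriction, "NOACs treatment can be initiated only in case of defined contraindication", and among the situations that open first-line use, "Individuals with higher sensitivity to warfarin are eligible for first line NOACs treatment in secondary prevention of stroke".

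**On the comparison.** Section 6 says the study was designed "to compare the healthcare resource use in patients who use warfarin or apixaban in secondary stroke prevention as a first line therapy". The primary objective in Section 7 is descriptive. The first secondary objective is "Comparison of direct costs related to warfarin/apixaban treatment during the first 6 months of the secondary stroke prevention in NVAF patients".

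**On the tests.** Section 8.7 calls the analyses descriptive and exploratory and bases all of them on every enrolled subject. It says that paired tests will be applied in the detailed analyses, that endpoints will be compared by differences in means, medians or proportions, and that significance is judged at 0.05. Sections 8.1 and 8.2 describe two separate cohorts, 120 patients on warfarin and 120 on apixaban, each followed for the 6 months after first prescription.

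**The concern.** There are two separate defects.

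**(A) Description of the cohorts.** The criterion that differs between the arms is not incidental. It concerns response to the comparator drug, and it is tied to which drug a patient could receive. A reader who relied on Section 8.9 would take the arms to be alike and read the cost difference as a like-for-like drug effect. The limitation as worded does not prevent that. Even if random is a slip for non-random, the sentence mentions neither genotype nor the reimbursement rule.

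**(B) Choice of test.** A paired test needs a rule that links each apixaban patient to one warfarin patient, or two measurements on the same patient. The plan supplies neither for the between-arm comparison. Taken literally, the instruction does not determine a p-value, and two analysts with the same data could report different ones.

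**Working it through.** **(A) The sections side by side**

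| Section 8.9 | Sections 8.2.1 and 6 |
|---|---|
| Both cohorts meet the same inclusion criteria | Criterion 4 binds 120 of 120 apixaban patients and 0 of 120 warfarin patients |
| No selection by subgroup | Apixaban patients are selected on a genetic subgroup |
| Main limitation is a random distribution over treatments | First-line access to apixaban depends on defined conditions, warfarin sensitivity among them |

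By design, sensitivity is 100% in the apixaban arm. In the warfarin arm it is not specified. Section 6 cites about 30% among healthy Czech subjects. If the warfarin-arm share is assumed to be 0%, 15% or 30%, the expected number is 120 × 0 = 0, 120 × 0.15 = 18 or 120 × 0.30 = 36, and the arms differ by 100, 85 or 70 percentage points. This is an imbalance in genotype. It is not an estimate of bias in cost, for which the documents give no input.

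**(B) Are there any pairs?**

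- Between patients: no matching variable or matching procedure appears anywhere in the plan.
- Within patients: Section 8.1 collects the 6 months after first prescription. Table 1 adds therapy between the index event and the index date, but there is no pre-treatment cost or outcome period.

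**What an arbitrary pairing would do to a paired t-test**

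From the plan: n = 120 per arm (Section 8.2) and the 0.05 level (Section 8.7). Assumed: two-sided testing, which the plan does not state, and equal SDs.

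1. Unpaired t at p = 0.050 with 2 × 120 − 2 = 238 df is 1.970.
2. For any row order, paired t = unpaired t / √(1 − r), where r is the chance correlation between the paired rows.
3. Over random orders, r has mean 0 and SD 1/√119 = 0.092, so 95% of orders have r within ±1.96 × 0.0917 = ±0.180.
4. The multiplier runs from 1/√1.180 = 0.921 to 1/√0.820 = 1.104.
5. Paired t runs from 1.970 × 0.921 = 1.814 to 1.970 × 1.104 = 2.175.
6. With 119 df, p runs from 0.072 to 0.032.

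Reordering one simulated normal data set 20,000 times gave the same range, with about 46% of orders below 0.05. One simulated skewed data set (lognormal, CV 1, an assumption) gave 0.030 to 0.071.

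**How far from 0.05 this matters.** The same formula gives 0.017 to 0.047 at an unpaired p of 0.03, and 0.055 to 0.108 at 0.08. Neither range crosses 0.05. The critical paired t is 1.980, so the range straddles 0.05 only when the unpaired t lies between 1.980/1.104 = 1.793 and 1.980/0.921 = 2.150, that is, for an unpaired p of about 0.033 to 0.074.

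**Unequal arms.** If one arm ended at 100 and the other at 120 (an illustration), a one-to-one paired test would leave out 120 − 100 = 20 patients. Section 8.7 says all analyses use all enrolled subjects.

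**The case against.** The strongest reply is that the study is exploratory, that criterion 4 and the access rule are stated openly in Sections 8.2.1 and 6, and that the primary objective is description within each arm. All three points are true, and they limit the stakes. They do not make Section 8.9 correct, and they do not define a test. Section 7 still lists a between-arm cost comparison, and Section 8.7 still sets a significance level for it.

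A second reply is that paired is probably a slip for two-sample or pairwise, since the next sentence of Section 8.7 speaks of differences in means, medians or proportions. That is quite possible. The repair is then a change of wording, but it is still needed, because the text does not say so and Annex 1 lists no stand-alone document that might.

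A third reply is that the calculation starts from a p-value placed exactly on the threshold. That is fair. For the t-test, the effect on the verdict is confined to the narrow band shown above.

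A reader might also infer more than the documents support:

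- *That the comparison is biased toward one drug.* The documents give no figure from which a size or direction could be derived.
- *That the paired tests inflate the type I error.* Nothing here shows that. The fault is an undetermined p-value.
- *That the plan expects an arm to fall short.* Section 8.2 says collection may be extended to 6 months, but not what follows if an arm is still under 120.
- *That the plan rules out adjustment.* Section 8.7 is silent on it, and its detailed analyses are not defined.

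**Conclusion.** Both defects stand and should be fixed.

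(A) Section 8.9 is wrong as written on the inclusion criteria and on the absence of subgroup selection, and its stated limitation does not disclose how patients came to receive apixaban. The secondary cost comparison cannot be attributed to the drug alone. That holds whether the intended contrast is between drugs in similar patients or between the two strategies as used under Czech rules; the plan does not say which. No bias size is claimed.

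(B) The test named in Section 8.7 has no defined pairs. Under the stated assumptions, an unpaired t-test p of 0.050 corresponds to a paired p of about 0.032 to 0.072, depending only on how unrelated patients are lined up. The practical consequence is a result that cannot be reproduced, with a changed verdict only near the threshold.

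The primary objective is untouched by either defect.

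**What to change.** **Section 8.9.** Replace the claims of identical criteria and no subgroup selection, and the stated limitation, with text such as: *The arms differ by inclusion criterion 4, which selects apixaban patients on genetic sensitivity to warfarin and does not apply to warfarin patients. Treatment was not randomly allocated; access to apixaban followed genotype and reimbursement conditions. Between-arm differences are exploratory and cannot be attributed to the drug alone.*

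**Section 8.7.** Replace paired tests with independent-group comparisons suited to skewed costs, for example the difference in mean cost with a bootstrap 95% CI, a rank-sum test, and Fisher's exact test for proportions. If matching was intended, define the matching variables and the handling of unmatched patients, and reconcile both with the full analysis set.

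**Optional.** An adjusted difference may be reported beside the crude one. It should use only variables fixed at or before the index date: age, sex, BMI, and days from index event to index date. CHA2DS2-VASc and HAS-BLED qualify only if dated at or before the index date, because Table 1 gives both the role of outcome with no measurement time, and later values could reflect treatment. The report should say that adjustment does not remove the genotype difference. Neither defect needs this analysis to be cured.

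**Cost.** The two required changes are to wording and need no new data. The downside is slightly more analysis work and a more modest comparative conclusion.

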## 8.10. Other aspects

Not applicable.

# 9. PROTECTION OF HUMAN SUBJECTS

## 9.1. Patient Information

All parties will comply with all applicable laws, including laws regarding the implementation of organizational and technical measures to ensure protection of patient personal data. Such measures will include omitting patient names or other directly identifiable data in any reports, publications, or other disclosures, except where required by applicable laws.

The personal data will be stored at the study site in encrypted electronic form and will be password protected to ensure that only authorized study staff has access. The study site will implement appropriate technical and organizational measures to ensure that the personal data can be recovered in the event of disaster. In the event of a potential personal data breach, the study site shall be responsible for determining whether a personal data breach has in fact occurred and, if so, providing breach notifications as required by law.

To protect the rights and freedoms of natural persons with regard to the processing of personal data, when study data are compiled for transfer to Pfizer and other authorized parties, patient names will be removed and will be replaced by a single, specific, numerical code, based on a numbering system defined by Pfizer. All other identifiable data transferred to Pfizer or other authorized parties will be identified by this single, patient-specific code. The investigator site will maintain a confidential list of patients who participated in the study,

linking each patient's numerical code to his or her actual identity. In case of data transfer, Pfizer will maintain high standards of confidentiality and protection of patients' personal data consistent with the Clinical Study Agreement and applicable privacy laws.

## **9.2. Patient Consent**

As this study involves anonymized structured or unstructured data, which according to applicable legal requirements do not contain data subject to privacy laws, obtaining informed consent from patients by Pfizer is not required.

## **9.3. Patient Withdrawal**

Not Applicable.

## **9.4. Institutional Review Board (IRB)/Independent Ethics Committee (IEC)**

The study will be reviewed by Independent Ethics Committee of the study site.

## **9.5. Ethical Conduct of the Study**

The study will be conducted in accordance with legal and regulatory requirements, as well as with scientific purpose, value and rigor and follow generally accepted research practices described in Guidelines for Good Pharmacoepidemiology Practices (GPP) issued by the International Society for Pharmacoepidemiology (ISPE), Good Epidemiological Practice (GEP) guidelines issued by the International Epidemiological Association (IEA), Good Practices for Outcomes Research issued by the International Society for Pharmacoeconomics and Outcomes Research (ISPOR), International Ethical Guidelines for Epidemiological Research issued by the Council for International Organizations of Medical Sciences (CIOMS), European Medicines Agency (EMA) European Network of Centres for Pharmacoepidemiology and Pharmacovigilance (ENCePP) Guide on Methodological Standards in Pharmacoepidemiology, and FDA Guidance for Industry: Good Pharmacovigilance and Pharmacoepidemiologic Assessment, FDA Guidance for Industry and FDA Staff: Best Practices for Conducting and Reporting of Pharmacoepidemiologic Safety Studies Using Electronic Healthcare Data Sets, Guidance for Industry: Patient-Reported Outcome Measures: Use in Medical Product Development to Support Labeling Claims and/or equivalent.

## **10. MANAGEMENT AND REPORTING OF ADVERSE EVENTS/ADVERSE REACTIONS**

This study protocol requires human review of patient-level unstructured data; unstructured data refer to verbatim medical data, including text-based descriptions and visual depictions of medical information, such as medical records, images of physician notes, neurological scans, X-rays, or narrative fields in a database. The investigator is obligated to report adverse events (AE) with explicit attribution to any Pfizer drug that appear in the reviewed

information (defined per the patient population and study period specified in the protocol). Explicit attribution is not inferred by a temporal relationship between drug administration and an AE, but must be based on a definite statement of causality by a healthcare provider linking drug administration to the AE.

The requirements for reporting safety events on the non-interventional study (NIS) adverse event monitoring (AEM) Report Form to Pfizer Safety are as follows:

- All serious and non-serious AEs with explicit attribution to any Pfizer drug that appear in the reviewed information must be recorded on the the e-CRF and reported, within 24 hours of awareness, to Pfizer Safety using the NIS AEM Report Form
- Scenarios involving drug exposure, including exposure during pregnancy, exposure during breast feeding, medication error, overdose, misuse, extravasation, lack of efficacy and occupational exposure associated with the use of a Pfizer product must be reported, within 24 hours of awareness, to Pfizer Safety using the NIS AEM Report Form.

For these safety events with an explicit attribution to or associated with use of, respectively, a Pfizer product, the data captured in the medical record will constitute all clinical information known regarding these AEs. No follow-up on related AEs will be conducted.

All research staff members will complete the Pfizer requirements regarding training on the following: *“Your Reporting Responsibilities: Monitoring the Safety, Performance and Quality of Pfizer Products (Multiple Languages)”* and any relevant Your Reporting Responsibilities supplemental training. This training must be completed by research staff members prior to the start of data collection. All trainings include a “Confirmation of Training Certificate” (for signature by the trainee) as a record of completion of the training, which must be kept in a retrievable format. Copies of all signed training certificates must be provided to Pfizer.

## **11. PLANS FOR DISSEMINATING AND COMMUNICATING STUDY RESULTS**

In the event of any prohibition or restriction imposed (e.g., clinical hold) by an applicable competent authority in any area of the world, or if the investigator is aware of any new information which might influence the evaluation of the benefits and risks of a Pfizer product, Pfizer should be informed immediately.

In addition, the investigator will inform Pfizer immediately of any urgent safety measures taken by the investigator to protect the study patients against any immediate hazard, and of any serious breaches of this NI study protocol that the investigator becomes aware of.

### **13. LIST OF TABLES**

Table 1. Table of variables

Table 2. Table of descriptive analyses

### **14. LIST OF FIGURES**

None.

### **15. ANNEX 1. LIST OF STAND ALONE DOCUMENTS**

None.

### **ANNEX 2. ENCEPP CHECKLIST FOR STUDY PROTOCOLS**

Not applicable.

### **ANNEX 3. ADDITIONAL INFORMATION**

Not applicable.
